6. PROCEDURES

Part 1

A trial nurse will receive all children who could have severe malaria and are potentially eligible to participate in the study and call the attending physician. The diagnosis of *falciparum* malaria will be made by a PfHRP2-based rapid malaria test. If the test is positive, and there is a clinical judgement that the patient has severe disease (according to a check list provided in the Case Report Forms [CRFs]), the patient can be enrolled, provided written informed consent has been obtained and all eligibility confirmed. The screening sequence will differ for patients with hyperparasitaemia only with no symptoms of severe malaria, as their eligibility will be determined when microscopy results are available, if performed.

Once the patient is enrolled, the randomisation deciding the drug allocation will be carried out. This is done in the following way: The next in a series of numerically sequenced envelopes is opened. The envelope will contain the unique participant number. From the moment the envelope is opened the patient is considered in the study whether or not the protocol is followed correctly thereafter. The envelope contains a slip of paper with a treatment box code number. The treatment box with this code number is then opened.

With the help of the study nurse, the attending physician will take the patient's history, and do a physical exam, where the list in the Case Report Forms (CRFs) serves as a guideline. Parameters include basic demographic parameters, questions regarding the previous history and current history, vital signs, coma score, and others. Patient monitoring during admission: to assure the best possible treatment of each study patient the following variables will be monitored based on WHO guidelines²¹

A detailed monitoring sheet will outline the planned observations and their frequency. In case of abnormal findings staff will be trained to repeat the test and to inform the key decision makers regarding the need to change the management of the patient. To help the treating physician, a practical guideline on the treatment of severe malaria (appendix 4) will be provided to all involved physicians.

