8.1 Definitions

8.1.1. Adverse Event (AE)

An AE is any undesirable event or clinical deterioration that occurs to a study participant during the course of the study; that is, from the time of administration of study drugs until study ends (i.e., until the follow up visit) whether or not that event is considered related to the study drugs, or to a concomitant drug or procedure, e.g.

- any unfavourable and unintended symptom
- physical sign
- abnormal laboratory result
- an illness
- any pre-existing condition that has worsened in grade

Any new clinical sign or clinical deterioration that occurs between signing the consent form and the administration of study drugs is not an AE. This information will be recorded in the medical records, as a pre-existing condition.

Condition associated with severe malaria

Common conditions resulting from a deterioration of severe malaria as per list should not be considered or reported as Adverse Events. They are recorded in the specific section of the CRF.

A list of the most common conditions in severe malaria includes,

- Deterioration of BCS or GCS
- Coma not present at admission
- Convulsions not present at admission
- Posturing not present at admission
- Decompensated shock (children systolic BP <70 mm Hg)
- Compensated shock (capillary refill >3sec /temperature gradient)
- Respiratory distress
- Hypoglycaemia (glucose <3 mmol/L)
- Severe anaemia
- Severe bleeding (requiring blood transfusion)
- Hemoglobinuria
- Severe jaundice
- Renal failure (urine output <0.5 mL/kg/hr >24 hours)

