3.2 Demographics and other baseline characteristics

The following baseline characteristics will be described by study arm in table 1 (below). Variables such as age, heart rate, respiratory rate will be summarized using median and interquartile range. Continuous variables such as weight, height, systolic and diastolic blood pressure, , haemoglobin will be summarized using mean \pm standard deviation. Parasitaemia at baseline will be described as geometric mean and range. Categorical variables such as sex, presence of fever and gametocytaemia at baseline will be summarized using frequencies and percentages.

Table 1. Baseline Characteristics of the Patients

Characteristics	1-STEP AS (N=XXX)	2-STEP AS (N=XXX)	Total (N=XXX)
Age (years), med (IQR)	XX.X (XX.X-XX.X)	XX.X (XX.X-XX.X)	XX.X (XX.X-XX.X)
Male sex, n (%)	XX (XX.X)	XX (XX.X)	XX (XX.X)
Weight (kg), mean (SD)	XX.X (XX.X)	XX.X (XX.X)	XX.X (XX.X)
Height (cm) mean (SD)	XX.X (XX.X)	XX.X (XX.X)	XX.X (XX.X)
Hb (g/dL), mean (SD)	XX.X (XX.X)	XX.X (XX.X)	XX.X (XX.X)
Parasites/ μ L, geometric mean (range)	XX.X (XX.X-XX.X)	XX.X (XX.X-XX.X)	XX.X (XX.X-XX.X)
Impaired consciousness or unrousable coma, n (%)	XX (XX.X)	XX (XX.X)	XX (XX.X)
Prostration, n (%)	XX (XX.X)	XX (XX.X)	XX (XX.X)
Failure to feed and drink without assistance, n (%)	XX (XX.X)	XX (XX.X)	XX (XX.X)
Multiple convulsions, n (%)	XX (XX.X)	XX (XX.X)	XX (XX.X)
Deep breathing, respiratory distress, n (%)	XX (XX.X)	XX (XX.X)	XX (XX.X)
Circulatory collapse or shock, systolic BP < 70 mmHg, n (%)	XX (XX.X)	XX (XX.X)	XX (XX.X)
Clinical jaundice plus evidence of other vital organ dysfunction, n (%)	XX (XX.X)	XX (XX.X)	XX (XX.X)
Haemoglobinuria, n (%)	XX (XX.X)	XX (XX.X)	XX (XX.X)
Suspected pulmonary oedema, n (%)	XX (XX.X)	XX (XX.X)	XX (XX.X)

STATISTICAL ANALYSIS PLAN

Renal failure (< 20 ml urine per hour) , n (%)	XX (XX.X)	XX (XX.X)	XX (XX.X)
Spontaneous bleeding/disseminated intravascular coagulation, n (%)	XX (XX.X)	XX (XX.X)	XX (XX.X)
Several episodes of vomiting in the preceding 24 hrs, n (%)	XX (XX.X)	XX (XX.X)	XX (XX.X)
Severe pallor with respiratory distress OR HCT<15% OR hb<5.0g/dl, n (%)	XX (XX.X)	XX (XX.X)	XX (XX.X)

3.3 Convenience and rapidness of administration of 1-step vs. conventional 2-step parenteral artesunate formulations and Costs of administration of 1-step vs. conventional 2-step parenteral artesunate formulations
Primary objective

To assess:

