Safety data will be presented in tabular and/or graphical format and summarized descriptively. Any clinically relevant abnormalities or values of potential clinically concern will be described. Patients will be analysed following the intention to treat analysis. All adverse event summaries will refer to treatment emergent adverse events, i.e. adverse events that newly started or increased in intensity after the study drug administration. Adverse events will be graded according to Common Terminology Criteria for Adverse Events (CTCAE). The safety and tolerability summaries will be presented in table 5.

Table 5 Incidence of adverse events within first 28 days by study arm

	1-STEP AS	2-STEP AS	p-value
Number of subjects	XX	XX	
Serious adverse events (SAEs), n/N, (%)	XX	XX	X.XXX
Possible, probable or definite drug related SAEs, n/N, (%)	X/XX (X.X)	X/XX (X.X)	X.XXX
Neurological sequelae at discharge	X/XX (X.X)	X/XX (X.X)	X.XXX
Neurological sequelae at 28	X/XX (X.X)	X/XX (X.X)	X.XXX
Neurological sequelae persisting at end of follow up	X/XX (X.X)	X/XX (X.X)	X.XXX
Grading of adverse events, n/N, (%)	1-2	3-4	1-2
Symptoms			
Impaired consciousness or unrousable coma, n (%)	X/XX (X.X)	X/XX (X.X)	X/XX (X.X)
Prostration, n (%)	X/XX (X.X)	X/XX (X.X)	X/XX (X.X)
Failure to feed and drink without assistance, n (%)			
Multiple convulsions, n (%)			
Deep breathing, respiratory distress, n (%)	X/XX (X.X)	X/XX (X.X)	X/XX (X.X)
Circulatory collapse or shock, systolic BP < 70 mmHg, n (%)	X/XX (X.X)	X/XX (X.X)	X/XX (X.X)
Clinical jaundice plus evidence of other vital organ dysfunction, n (%)	X/XX (X.X)	X/XX (X.X)	X/XX (X.X)
Haemoglobinuria, n (%)	X/XX (X.X)	X/XX (X.X)	X/XX (X.X)
Suspected pulmonary oedema, n (%)	X/XX (X.X)	X/XX (X.X)	X/XX (X.X)

STATISTICAL ANALYSIS PLAN

	X/XX (X.X)	X/XX (X.X)	X/XX (X.X)	X/XX (X.X)	X.XXX
Renal failure (< 20 ml urine per hour) , n (%)	X/XX (X.X)	X/XX (X.X)	X/XX (X.X)	X/XX (X.X)	X.XXX
Spontaneous bleeding/disseminated intravascular coagulation, n (%)	X/XX (X.X)	X/XX (X.X)	X/XX (X.X)	X/XX (X.X)	X.XXX
Several episodes of vomiting in the preceding 24 hrs, n (%)	X/XX (X.X)	X/XX (X.X)	X/XX (X.X)	X/XX (X.X)	X.XXX
Severe pallor with respiratory distress OR HCT<15% OR hb<5.0g/dl, n (%)	X/XX (X.X)	X/XX (X.X)	X/XX (X.X)	X/XX (X.X)	X.XXX
Total	X/XX (X.X)	X/XX (X.X)	X/XX (X.X)	X/XX (X.X)	X.XXX
Laboratory abnormalities					
Creatinine	X/XX (X.X)	X/XX (X.X)	X/XX (X.X)	X/XX (X.X)	X.XXX
Total bilirubin	X/XX (X.X)	X/XX (X.X)	X/XX (X.X)	X/XX (X.X)	X.XXX

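### SAP Table 5 reuses the baseline severity labels as post-dose event rows, so a single new convulsion, compensated shock and hypoglycaemia have no row by arm

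*SAP*

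**What the plan says.** SAP 3.2 presents the clinical severity list as a description of patients at entry: "The following baseline characteristics will be described by study arm in table 1 (below". SAP 3.5 then plans a comparison of AE and SAE frequencies between arms, gives special weight to a set of severe-malaria variables, and lays out Table 5 for the first 28 days. Its AE summaries are restricted to treatment-emergent events, and the symptom rows are split by grade (1-2 and 3-4). Those rows include "Multiple convulsions, n", "Circulatory collapse or shock, systolic BP < 70 mmHg, n" and "Spontaneous bleeding/disseminated intravascular coagulation, n".

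Protocol 8.1.1 has a different list, of conditions that arise when severe malaria deteriorates. They are not to be reported as AEs and go into a dedicated section of the CRF. The list includes "Convulsions not present at admission", with no minimum number, as well as "Decompensated shock (children systolic BP <70 mm Hg", "Compensated shock (capillary refill >3sec /temperature gradient" and hypoglycaemia, defined as glucose below 3 mmol/L. Protocol 6.5 leaves most in-hospital monitoring to good medical practice but fixes that of glucose: on admission, then every 4 to 6 hours for at least 24 hours.

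The SAP assigns no table to that CRF section.

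**The concern.** Labels written to describe a child on arrival are used to define events after dosing. The vomiting row shows this most clearly. It looks back over the previous 24 hours, which has a meaning at admission but none as a 28-day event.

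Protocol 3.2 says the new formulation has not yet been deployed in severe malaria and undertakes to document its safety accurately. Table 5 is the only SAP table that sets out clinical deterioration after dosing by arm. If it is followed as written, three conditions that the protocol says are recorded have no row in which the arms can be compared, and the table cannot be reconciled with the CRF section that holds those data.

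**Working it through.** No figure in the plan bears on this point, so the check is a comparison of texts.

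**Step 1. Table 5 against Table 1.** The 13 symptom rows of Table 5 carry the same labels as the 13 clinical severity rows of Table 1, including the vomiting look-back (13 of 13).

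**Step 2. Table 5 against protocol 8.1.1, for the items in question.**

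| Condition | SAP Table 5 | Protocol 8.1.1 | Result |
|---|---|---|---|
| Convulsions | Multiple only | Any that is new since admission | Table 5 is narrower; a single new convulsion has no row |
| Shock, decompensated | Systolic BP below 70 mmHg | Systolic BP below 70 mmHg | Same cut-off |
| Shock, compensated | None | Capillary refill over 3 seconds or temperature gradient | No row |
| Hypoglycaemia | None | Glucose below 3 mmol/L | No row |
| Bleeding | Spontaneous bleeding or DIC, no transfusion condition | Severe, needing transfusion | Different; Table 5 is broader |
| Jaundice | Clinical jaundice with dysfunction of another vital organ | Severe, no threshold given | Different; direction cannot be determined |

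New posturing, also on the protocol list, has no row of its own either. The renal-failure rows differ as well: below 20 ml per hour in Table 5, and below 0.5 mL/kg/hr for more than 24 hours in the protocol. The two hourly rates coincide only at 20 / 0.5 = 40 kg. That is a related mismatch outside this point.

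**Step 3. Could the three conditions appear elsewhere in Table 5?** The laboratory rows are creatinine, total and direct bilirubin, ALT, AST, alkaline phosphatase and haematocrit; glucose is absent. The SAE rows would take in an event only if it were reported as serious. The remaining route is the general statement that clinically relevant abnormalities will be described. Neither route guarantees a count by arm of single convulsions, compensated shock or hypoglycaemia.

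**Step 4. Would rewording the Table 5 rows be enough?** No. Table 5 is titled and graded as an AE table. The protocol (sections 8 and 8.3.1) requires CTCAE grading of adverse events, and 8.1.1 takes its listed conditions out of AE reporting. Nothing says that they are graded. Putting the protocol list into the graded AE rows would leave both the data source and the grade columns unresolved.

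**The case against.** The strongest reply is that the protocol list is an exclusion list. A reader might infer that 8.1.1 supplies the AE definitions that Table 5 should have applied. It does not: it says these conditions, when they result from deterioration of severe malaria, are not AEs. This stands, and it is why the remedy cannot be new wording inside the AE rows. It does not remove the gap, because the same paragraph sends these conditions to their own CRF section, for which the SAP has no table.

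Other stronger readings also fail:

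- **Entry criteria.** A reader might say that Table 5 applies the trial's entry criteria. The SAP calls the Table 1 list baseline characteristics. Severity for enrolment is judged "according to a check list provided in the Case Report Forms", and that list is not reproduced in the documents.
- **Wrong shock threshold.** The 70 mmHg figure is the protocol's own for decompensated shock. Only the compensated category lacks a row.
- **Undercounted bleeding and jaundice.** The Table 5 bleeding row needs no transfusion, so replacing it with the protocol item would drop non-transfused bleeds. For jaundice the protocol gives no threshold, and Table 5 has bilirubin rows.
- **Events not counted at all.** This is too strong. Protocol 8.2 provides for SAEs resulting from deterioration, so a serious event can reach the SAE rows, and narrative description is planned.
- **A large loss of events or power.** The documents give no rate of new convulsions after dosing and do not say what number counts as multiple. The one figure, convulsions in up to 80% of children with cerebral malaria (protocol Appendix 4), describes something else. Any missed share or power figure would rest on assumed rates.

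Safety is also exploratory in the protocol, is summarised descriptively, and is stated not to be powered for formal comparison. This limits the weight of the point.

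**Conclusion.** The point holds in a limited form. All 13 symptom rows of Table 5 are baseline labels carried over, and they do not match the on-study items of protocol 8.1.1. Three conditions that the protocol says are recorded (a single new convulsion, compensated shock and hypoglycaemia) have no dedicated row by arm. Bleeding and jaundice are mismatches of definition without a shown undercount.

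The number of children affected cannot be estimated from the documents, and no loss of power is claimed. The conclusion assumes that the CRF section contains the items as protocol 8.1.1 lists them, since the CRF itself is not shown. It also assumes that the table layouts in SAP 3.5 are the full planned safety output. The point is worth acting on because the data are said to be collected already, but it remains a reporting gap in an exploratory comparison. It does not affect the co-primary endpoints.

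**What to change.** Add to SAP 3.5 a separate, ungraded block by arm for conditions associated with severe malaria that arise after the first dose. Name the protocol 8.1.1 CRF section as its source and use the protocol items as rows. Include any convulsion not present at admission, decompensated and compensated shock as two rows, and hypoglycaemia below 3 mmol/L. Keep the broader bleeding row alongside the protocol's transfusion item, so that non-transfused bleeds are not lost. Confine the other baseline labels, including the 24-hour vomiting look-back, to Table 1.

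Reconcile protocol 8.1.1 with SAP 3.5 on whether these conditions are tabulated as AEs, and state the answer in the SAP so that no event is drawn from two sources.

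The cost is a short SAP amendment and a few extra descriptive rows. It needs no new data collection and no change to patient care.
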